7.1. Descriptive methods

- Descriptive analysis of qualitative and ordinal variables will comprise the count and the frequency of each category.

- Descriptive analysis of quantitative variables will be presented by the mean and standard deviation (SD) for the data that follows a Gaussian distribution and the median and range otherwise.
- The 95% confidence intervals will be presented for main endpoints. The ‘exact’ Clopper-Pearson confidence interval will be provided to assess 2-sided 95% confidence interval for main binomial proportions (e.g. ORR rate).
- The number of missing values will be reported in the results table for each variable.

7.2. Comparative methods

- For two groups of normal distribution, the means of quantitative variables will be compared using the Student’s t- test if the assumption of homogeneity of variance is verified (the Satterthwaite method will be used if the variances are unequal).
- If more than two groups have to be compared, analysis of variance (ANOVA) will be performed for quantitative variables if normality in each group and homoscedasticity are met. Homogeneity of variances will be tested by Levene's test.
- If the assumptions are not verified, alternative parametric testing such as Mann Whitney Wilcoxon and Kruskal-Wallis tests will be applied.
- The association between two qualitative variables will be assessed with the Pearson’s Chi-square test. When the number of values will be less than 5, groups of categories will be proposed or the Fisher’s exact test will be performed.
- For all tests performed, the significance level will be 5%.

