2.3. Study Objectives

- Primary Objective:
 - To assess the impact of SU treatment on Progression Free Survival (PFS) and on Time to Treatment Failure (TTF) for patients with adv/ mRCC.
- Secondary Objectives:
 - To assess the Objective Response Rate (ORR) for adv/ mRCC patients receiving SU as 1st line treatment.
 - To describe the usage of different doses of SU in these patients in terms of: dosing change, dosing schedules and the average dose received during the SU period treatment
 - To assess the impact of the 2nd line sequence SU- different treatment on combined PFS and TTF for patients with adv/mRCC and according to the second line post SU treatment (TK1,mTOR)
 - To describe the safety of 2nd line SU-different sequence treatment and the tolerability of patients receiving it.
 - To measure Quality of Life (QoL) of the patients
 - The following treatment outcomes will also be assessed:
 - Treatment patterns (dose/ duration) for SU
 - Patterns of toxicity exhibited by patients

3. Interim and Final Analysis

- A final report will address the study objectives through detailed analysis of the efficacy and safety endpoints as advised by the protocol.
- There will be no interim analysis for this study.

4. Hypothesis and Decision Rules

- Descriptive and hypothesis testing will be applied for presenting and analysis data
- For all comparisons, the significance threshold will be set at the commonly used 5% level. The type I error will not be adjusted for multiplicity
- Summary tables will contain footnotes in the body of the title that reference any data listings or tables associated with the table or figure (e.g. Reference: Listing 16.X.XX).
- All means and medians will be formatted to one more decimal place than the measured value. Confidence intervals and standard deviation values will be formatted to two more decimal places than the measured value. Minimum and maximum values will be presented with the same number of decimal places as the measured value.
- The number and percentage of responses will be presented in the form XX (XX %) where the percentage as whole numbers will be in parentheses.
- All p-values will be presented with at least 3 decimal places ensuring meaningful representation.

- All summary tables will include the total number of subjects in the population that is being analysed
- Analysis population and subgroups

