4.2. Subgroups

4.2.1. Subgroups to meet primary and secondary objectives

- Compare efficacy parameters (PFS, OS) for the combined 1st line SU- 2nd line sequences according to the second line post SU :
 - SU in 1st line-Axitinib TKI in 2nd line
 - SU in 1st line- other TKI in 2nd line (sorafenib, pazopanib)
 - SU in 1st line/mTOR in 2nd line (temsirolimus, everolimus)

CCI [REDACTED]

- [REDACTED]
- [REDACTED]
- [REDACTED]
- [REDACTED]
- [REDACTED]

[figure not shown] 2);

- Incidence of other AEs (grade ≤ 2);
- Incidence of all AE per grade.
- AEs will be analyzed separately for AEs related to SU as solicited and unsolicited AE.
- **Discontinuation due to toxicity**
 - Proportion of patients who discontinued the treatment of interest, because of AEs;
 - Treatment duration until discontinuation for AEs;
- **Deaths**
 - Proportion of patients who died due to any cause, over the treatment period (including the 28 days after the treatment discontinuation) and along the study;
 - Cause of death (tumor-related, other cause).

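### SAP 7.2 lets a variance check choose between Student's and the Satterthwaite t-test; in small unequal groups where the smaller is more variable, the 5% level can become about 7-10%

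*SAP*

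**What the plan says.** SAP 7.2 (Comparative methods) sets the rules for comparing quantitative variables between groups.

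- Two normally distributed groups: Student's t-test applies "if the assumption of homogeneity of variance is verified (the Satterthwaite method will be used if the variances are unequal"). The bullet does not say how homogeneity is to be verified, or at what threshold.
- More than two groups: "If more than two groups have to be compared, analysis of variance (ANOVA) will be performed for quantitative variables", subject to normality and equal variances. Here a check is named: "Homogeneity of variances will be tested by Levene's test".
- A third bullet sends comparisons whose assumptions fail to Mann-Whitney-Wilcoxon or Kruskal-Wallis. For two groups with unequal variances this overlaps with the Satterthwaite instruction.

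On the error level, SAP section 4 states "For all comparisons, the significance threshold will be set at the commonly used 5% level" and "The type I error will not be adjusted for multiplicity". Section 7.2 repeats the 5% level for every test performed.

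**The concern.** Treating equal variance as verified when a preliminary test is not significant takes absence of evidence as evidence of equality. In small groups such a test has limited power. If it misses a real difference and the smaller group is the more variable one, the pooled variance is dominated by the larger, less variable group. The standard error is then too small, and Student's test rejects too often.

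Small, unequal groups are plausible here. The study plans 140 patients, treatment follows routine practice, and the second-line pools (axitinib, other TKI, mTOR inhibitor, supportive care) are not balanced by design. What is at stake is whether a two-group comparison of means reported at 5% was really made at 5%.

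**Working it through.** **Inputs from the documents.** Level 5% per test, no multiplicity adjustment (SAP 4 and 7.2); 140 patients and an assumed ORR below 37% (protocol 8.7); the selection rule (SAP 7.2).

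**Inputs that are assumptions.** Group sizes, SDs and which group is more variable (none is given); two-sided testing; mean-centred Levene's test at 5% as the two-group check. Data are normal, which is the condition 7.2 sets for this branch.

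**Formulas.** With v1 = s1²/n1 and v2 = s2²/n2:
- Student: standard error √[sp²(1/n1 + 1/n2)], where sp² = [(n1−1)s1² + (n2−1)s2²]/(n1+n2−2), on n1+n2−2 degrees of freedom.
- Satterthwaite: standard error √(v1+v2), on (v1+v2)² / [v1²/(n1−1) + v2²/(n2−1)] degrees of freedom.
- Rule simulated: Student if Levene's p is 0.05 or more, otherwise Satterthwaite.

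**Step 1: the stated 5%.** With equal SDs and equal means, 60,000 runs per size pair gave 4.8-5.1% for Student. The stated level is reproduced when its assumption is true.

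**Step 2: why the direction matters.** Take 8 vs 40.
- Smaller group SD 1.5, larger group SD 1. True variance of the difference: 2.25/8 + 1/40 = 0.306. Variance Student expects: [(7×2.25 + 39×1)/46] × (1/8 + 1/40) = 1.190 × 0.15 = 0.179. The true standard error is √(0.306/0.179) = 1.31 times the one used. The critical value 2.013 acts like 2.013/1.31 = 1.54, a false-positive rate of roughly 13% if Student were always used.
- SDs reversed. True variance: 1/8 + 2.25/40 = 0.181. Student expects [(7×1 + 39×2.25)/46] × 0.15 = 2.060 × 0.15 = 0.309. The standard error used is too large, so the test is conservative.

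**Step 3: the selection rule under equal means, smaller group more variable** (60,000 runs each; simulation standard error about 0.1 point).

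| Sizes | SD ratio | Levene misses | Selection rule | Always Satterthwaite |
|---|---|---|---|---|
| 8 vs 40 | 1.3 | 84% | 8.9% | 5.2% |
| 8 vs 40 | 1.5 | 70% | 10.3% | 5.1% |
| 10 vs 50 | 1.3 | 82% | 8.5% | 5.2% |
| 10 vs 50 | 1.5 | 64% | 9.6% | 5.1% |
| 15 vs 60 | 1.3 | 76% | 7.7% | 5.1% |
| 15 vs 60 | 1.5 | 54% | 8.1% | 5.1% |
| 20 vs 120 | 1.3 | 68% | 8.0% | 5.1% |
| 20 vs 120 | 1.5 | 39% | 7.6% | 4.9% |

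**Step 4: where the inflation disappears.**
- Same sizes and ratios, smaller group less variable: 3.0-4.0%.
- Equal sizes (20 vs 20): 4.8-5.2%.
- 52 vs 88 (the split at the protocol's ORR ceiling, 0.37 × 140 = 51.8): 5.5% at ratio 1.3 and 5.3% at ratio 1.5.

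**Step 5: what always using Satterthwaite costs.** Equal SDs, with the difference set so that Student has 80% power:

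| Sizes | Selection rule | Always Satterthwaite | Loss (points) |
|---|---|---|---|
| 8 vs 40 | 79.3% | 73.0% | 6.3 |
| 10 vs 50 | 79.6% | 74.9% | 4.7 |
| 15 vs 60 | 79.6% | 77.1% | 2.5 |
| 20 vs 120 | 79.7% | 77.4% | 2.3 |

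At 5 vs 20 the loss is about 10 points (78.7% to 68.7%), and Satterthwaite itself runs slightly high, at 5.4-5.9%.

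**The case against.** The strongest objection is that no visible analysis is shown to use this rule. PFS and OS by sequence are compared by log-rank and Cox methods (SAP 7.4, 8.1.1). ORR and safety are descriptive (8.1.2, 8.2). Quality of life uses descriptive methods and MMRM (8.3); the paired t-test in protocol 8.9 is not a two-group test. SAP 4.2.1 lists three second-line groups, so a joint comparison of means would fall under the ANOVA bullet, and dummy tables 9.1 and 9.3 have no p-value column. All of this stands. A reader might infer that the sequence comparisons of PFS or OS run at 10%; the documents do not support that. Blacked-out text cannot be counted either way.

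Three further objections also stand.
- A reader might take Levene's test as specified for two groups. The SAP names it only for more than two, so the simulated rule is partly an inference.
- It is tempting to say that the check usually misses a relevant difference. That depends on the case: at 20 vs 120 and ratio 1.5 it misses 39%. The direction of the imbalance is also assumed; the reverse is conservative.
- It is tempting to call the pre-test useless and its removal free. Step 5 shows a real power cost, largest where the inflation is largest.

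Finally, protocol 8.11 describes the study as hypothesis-generating, and the SAP openly leaves multiplicity unadjusted. That limits the consequence. It does not make a pre-test-dependent 5% level accurate.

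**Conclusion.** The point holds as a minor, conditional one. Section 7.2 makes the choice of test depend on an unspecified variance check while stating 5% for every test. With normal data, Levene's test at 5%, smaller groups of about 8-20 against clearly larger ones, and the smaller group's SD 1.3-1.5 times the larger's, a two-group comparison of means under this rule can run at about 7-10%. It runs at about 3-4% in the reverse direction and near 5% with equal or larger groups. Sizes, SDs and direction are assumptions. Only exploratory two-group comparisons of means made under 7.2 are affected; no primary or named secondary result in the visible plan is shown to be.

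**What to change.** In SAP 7.2, drop the homogeneity condition from the two-group bullet and use the Satterthwaite (unequal-variance) t-test for every two-group comparison of normally distributed means. Keep any homogeneity test as descriptive output that does not select the test. State that, for two groups, the non-parametric bullet is triggered by non-normality only, which removes its overlap with the Satterthwaite instruction.

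The edit is about one sentence, and the method is already named in the same bullet. The price is the power loss in step 5 when variances are truly equal: about 2-3 points in moderately unequal groups and about 5-7 points when the smaller group is 8-10. With groups of about 5 the level is slightly above nominal (about 5.5-6%), so comparisons that small are better reported as estimates with confidence intervals than as tests.

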7.3. Logistic regression model

- A logistic regression model will be used in case of multivariate model to analyze prognostic factors for a dichotomous variable (for example: ORR).
- The Hosmer-Lemeshow test will be used to test the adequacy of the logistic regression model.

7.4. Survival analysis methods

- The survival functions for PFS, TTF, TSF, and OS will be estimated with the Kaplan-Meier method. The survival function $S(t)$ is the probability that the event (treatment discontinuation, death or progression) does not occur before a specified time.
- This method will be applied to derive, survival curves, median event time and a 95% confidence interval for the median survival time (time at which half the analyzed patients have presented the event).
- Survival curves will give an idea of whether or not the groups are proportional (i.e. the survival functions are approximately parallel).
- For OS, the share of patients alive at 24 months will also be measured.
- The log-rank test of equality across strata will be used to compare survival curves for categorical variables (sub-groups of interest).
- For continuous variables, a univariate Cox proportional hazard regression will be used.
- For analyses of prognostic factors of survival time, multivariate Cox proportional hazard regressions will be performed.

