8.9. Data Analysis

Detailed methodology for summary and statistical analyses of data collected in this study will be documented in a Statistical Analysis Plan (SAP), which will be dated, filed and maintained by the sponsor. The SAP may modify the plans outlined in the protocol; any major modifications of primary endpoint definitions or their analyses would be reflected in a protocol amendment.

Demographic and other clinical characteristics of the patients will be summarized using the mean, standard deviation, median, minimum, and maximum values, for numeric variables such as age and duration of follow up and frequency distributions for categorical data such as gender. The median and 95% confidence intervals for the main outcomes PFS and TTF will be estimated using the method of Kaplan-Meier. The ORR for adv/mRCC patients receiving SU in the 1st line will be computed along with its 95% confidence interval using the Clopper-Pearson formula. Cox proportional hazard models may be used to explore the potential influences of baseline characteristics on PFS or TTF. A multiple logistic regression model can be used to assess the effect of prognostic variable on ORR.

Change in other variables such as Quality of life and weight at last visit as compared to the baseline will be assessed using the paired t-test at each visit in addition to computing mean differences along with 95% confidence intervals. Moreover, repeated methods can be used to look for trends over time and adjust for possible confounders.

All AEs occurring during the study will be considered as treatment-emergent, and the frequency of AEs will be summarized. Sub-group analyses of association between efficacy outcomes, safety measurements, and baseline factors will be performed for exploratory reasons as needed.

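### SAP 7.4 judges proportionality by parallel survival curves, which is not the proportional-hazards condition and can mislead the reading of the exploratory Cox models

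*SAP*

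**What the plan says.** SAP 7.4 estimates survival functions by Kaplan-Meier. It defines S(t) on the untransformed probability scale: it "is the probability that the event (treatment discontinuation, death or progression) does not occur before a specified time". Its only statement on proportionality is that the plotted curves will indicate whether it holds between groups, which it equates with the condition that "the survival functions are approximately parallel".

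Three methods follow in the same section:
- a log-rank comparison between subgroups formed by categorical variables;
- a univariate Cox model for each continuous variable;
- a joint model for prognostic factors, of which the section says that "multivariate Cox proportional hazard regressions will be performed".

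Protocol 8.9 describes the Cox work more loosely: "Cox proportional hazard models may be used to explore the potential influences of baseline characteristics on PFS or TTF". It states no check of the assumption.

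The readable text of both documents contains no log(-log S) plot, residual check or time-interaction term, and no action if proportionality fails. Parts of the SAP are blacked out, so a further check there cannot be excluded. It would not correct the sentence in 7.4.

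**The concern.** The sentence speaks of groups being proportional and does not use the word hazards. In a section that goes on to Cox models, proportional hazards is the only sensible reading, and the condition given for it is the wrong one. An analyst who follows the sentence may doubt a Cox model that fits well, or take comfort in one whose hazard ratio changes over time.

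It matters most for the prognostic-factor models. SAP 7.6 screens covariates univariately at p = 0.25 and then eliminates backward. A covariate whose effect changes with time can be dropped, or summarised by one average effect that describes no period well. Some candidates in SAP 5.5, such as age and number of metastatic sites, can enter as continuous terms, for which there are no group curves to compare.

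The SAP does plan assumption checks elsewhere: Shapiro-Wilk in section 7, Levene in 7.2 and Hosmer-Lemeshow in 7.3. The intention to verify is clear, and the survival check is the one that tests the wrong property.

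**Working it through.** The plan states no figure on this point, so the check is algebraic, with a numerical illustration.

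**Inputs.** Medians of 10.5 and 5.9 months are the durations of first-line sunitinib in academic and community practice quoted in Protocol 6.1.1. They come from two separate studies and are used for scale only. The exponential shape is an assumption.

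**1. Proportional hazards does not give parallel S(t).** With a constant hazard ratio h, S1(t) = S0(t)^h. Then log(-log S1) − log(-log S0) = log h at every t. The gap S0 − S0^h is 0 at t = 0, rises to a maximum where S0 = h^(−1/(h−1)), and then shrinks towards 0.

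Here h = 10.5/5.9 = 1.78, S0 = 0.5^(t/10.5) and S1 = 0.5^(t/5.9).

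| Month | S0 | S1 | Gap in S(t) | Gap in log(-log S) |
|---|---|---|---|---|
| 1 | 0.936 | 0.889 | 0.047 | 0.576 |
| 3 | 0.820 | 0.703 | 0.117 | 0.576 |
| 6 | 0.673 | 0.494 | 0.179 | 0.576 |
| 12 | 0.453 | 0.244 | 0.209 | 0.576 |
| 18 | 0.305 | 0.121 | 0.184 | 0.576 |
| 24 | 0.205 | 0.060 | 0.145 | 0.576 |

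The hazards are exactly proportional, yet the gap more than quadruples from month 1 to month 12 and then falls by about 30% by month 24 (0.145/0.209 = 0.69). On the log(-log S) scale the separation is constant at ln(1.78) = 0.576.

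**2. Parallel S(t) does not give proportional hazards.** Over an interval where S1 = S0 − c with c constant, the two densities are equal, so HR(t) = S0/(S0 − c). This rises as S0 falls. Both curves must start at 1, so the illustration lets the gap open linearly over months 0 to 3 and holds it constant after that. The ramp and the values of c are assumptions.

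| c | HR, month 3 | HR, month 12 | HR, month 24 |
|---|---|---|---|
| 0.10 | 1.14 | 1.28 | 1.95 |
| 0.15 | 1.22 | 1.50 | 3.72 |
| 0.20 | 1.32 | 1.79 | 40.3 |

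For c = 0.15 at month 12, 0.453/0.303 = 1.50. The last entry for c = 0.20 is extreme because S1 is then only 0.005. With c = 0.10 or 0.15 the hazard ratio still changes about 1.7-fold or 3.0-fold between months 3 and 24, although the survival curves are exactly parallel. The log(-log S) separation for c = 0.15 is 0.703, 0.411 and 0.604 at months 3, 12 and 24, so that scale shows the departure.

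**The case against.** The sentence is informal. It says the curves give an idea, asks only for approximate parallelism, sets no threshold and attaches no decision. Log-rank and Cox analyses are planned whatever the plot shows. A reader might infer that the SAP would reject proportional groups, accept non-proportional ones and so reach a wrong verdict in both directions. The text does not support that, because it contains no accept-or-reject step. This stands, and it is why the conclusion is that the check can mislead.

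By eye, truly proportional groups can also look roughly parallel once they have separated. With a hazard ratio of 1.25 and the same 10.5-month reference, the gap is 0.063, 0.081, 0.078 and 0.067 at months 6, 12, 18 and 24. With a hazard ratio of 0.6 it is 0.169, 0.185 and 0.181 at months 12, 18 and 24. On step curves from subgroups of 140 patients such differences would be hard to see. This also stands: the sentence will not always mislead, although the early separation is still not parallel.

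A reader might extend the point to the log-rank comparisons. That goes too far. The log-rank test is valid under its null hypothesis without proportional hazards; non-proportionality affects its power.

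Finally, the stakes are modest. Protocol 8.9 makes the Cox models optional and exploratory, Protocol 8.11 presents the study as hypothesis-generating, and the efficacy dummy table in SAP 9.3 has no hazard-ratio entry. All of this limits the size of the problem, but none of it makes parallel survival functions the right condition.

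**Conclusion.** The point holds as a technical error in SAP 7.4 with limited reach. Parallel untransformed survival functions are neither necessary nor sufficient for proportional hazards, apart from identical curves. That is algebra and rests on no assumption about the data. Only the size of the illustration depends on the assumed exponential shape, the borrowed medians and the chosen gaps.

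What is affected is the interpretation of the exploratory Cox models, including the variable selection in SAP 7.6. For continuous covariates the fault is that the stated check does not apply directly, so the readable text leaves them without one.

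A reader might infer that the main results are at risk. They are not: the PFS and TTF medians with their 95% confidence intervals are Kaplan-Meier estimates and do not use proportional hazards.

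**What to change.** Replace the sentence in SAP 7.4 with:

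> Proportional hazards will be assessed by whether log(-log S) curves are approximately parallel for categorical covariates, and by scaled Schoenfeld residuals or a covariate-by-time term for covariates kept in the Cox model. If the assumption is clearly violated, the model will be stratified on that covariate or its hazard ratio reported by period.

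No new data, visits or patients are needed; the cost is one sentence and a few extra plots or tests. With about 140 patients these checks have limited power to detect departures, so a non-significant result should not be reported as proof that the hazards are proportional.

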7.5. Analysis of longitudinal data

- Mixed models with Repeated Measures (MMRM) will be used to analyze longitudinal data (QoL over the SU treatment).
- These models will allow to meet questions as “Are there significant changes in the endpoint from baseline?” or “Do any groups differ at any time point regarding the endpoint?”
- Linear models will be used for dependent variables continuous, assumed to be normally distributed. The missing observations will be considered to be missing at random.
- MMRM will include the fixed, categorical effect of time, as well as the continuous, fixed covariates of the baseline value and baseline-by-time interaction. A significant baseline-by-time interaction would indicate that baseline levels predict change in dependent variable of interest over time.

